community fitness and will be inclusive of all individuals with chronic health conditions. Physical activity and exercise guidelines recommend everyone, including those with chronic health conditions, strive for 150 minutes of moderate intensity aerobic exercise per week.¹ This study will contribute to the knowledge of how patients achieve recommended individual HR and moderate-high intensity zones during exercise.

Aim 1: Measure the extent to which monitoring and education regarding intensity is provided (1) before HR monitoring intervention, (2) when providers know HR monitoring is occurring but without visual feedback, and (3) with visual feedback of HR monitoring.

We hypothesize providers will modify their behavior in the number of times they ask about intensity, adjust session intensity or provide education regarding intensity when visual feedback is provided compared to no feedback, which will be further increased from pre-study baseline levels.

Aim 2: Determine the efficacy of using HR with visual feedback during rehabilitation to reach target intensity.

We hypothesize participants will have higher mean HR and increased time in their individualized target HR zones when given visual feedback compared to no feedback during group sessions.

Aim 3: Determine the safety of using Heart Zones technology in rehabilitation for increasing participant exercise intensity.

We hypothesize the technology will be safe without an increase in number of adverse events throughout their rehabilitation stay.

Aim 4: Assess patient acceptability, exercise self-efficacy and confidence following use of Heart Zones technology in rehabilitation sessions.

We hypothesize use of Heart Zones technology in group settings with feedback will increase participant self-efficacy and confidence in reaching higher exercise intensities, and will be well accepted. Furthermore, we hypothesize the use of Heart Zones will be feasible in at least 75% of patient's group sessions.

Aim 5: Explore the feasibility of submax exercise testing when completed 2 times to establish individualized training targets for individuals receiving inpatient rehabilitation.

We hypothesize submax exercise testing will be feasible to perform, safe and informative to clinicians to establishing individualized heart rate zones. We believe there will be a change pre to post in submax testing indicating improvement in patient's condition.

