Clinical providers have many options for submaximal (submax) aerobic capacity testing, although they are rarely used outside of cardiac rehabilitation. The 6 minute walk test which have been studied in a range of populations including heart failure, end stage lung disease, COPD, chronic renal failure, and older individuals.¹⁵ The recumbent stepper test has been shown to be able to predict VO₂ peak in healthy adults.¹⁶ For individuals with limited ambulatory or lower extremity motor function, an alternative to determine aerobic capacity is to use the arm crank ergometer.¹⁷

This study will facilitate the understanding of feasibility and safety of moderate to vigorous aerobic endurance exercise, based on individually set aerobic intensity zones carried out in a rehabilitation setting. It will also study if the behavior of the provider or participant changes when provided visual feedback of HR during sessions.

STUDY ENDPOINTS:

[figure not shown]
- To evaluate the safety of using Heart Zones technology in a rehabilitation model across the rehabilitation continuum by recording the incidence of adverse events.
- To demonstrate the feasibility of using Heart Zones during group sessions by measuring the incidence of session usage to missed sessions.
- To demonstrate the efficacy of using visual feedback of HR monitoring to achieve greater intensities during sessions compared to no visual feedback of HR.
- To analyze the effect of HR monitoring with visual feedback on therapist perception of acceptability, feasibility and appropriateness as well as participant exercise self-efficacy and confidence.
- To assess feasibility of submax exercise testing in the inpatient setting to establish individualized target training intensities and assess the change in submax testing when completed at 2 times points.

STUDY INTERVENTION(S) / INVESTIGATIONAL AGENT(S):

Heart Zones is a commercially available software platform that integrates feedback from several different commercially available HR sensors. The software platform displays HR and provides continuous biofeedback with ability to provide individualized programs to maximize individual and multi-person sustained effort. It has the capability to record session data for later review and analysis.

We are not evaluating safety or effectiveness of the Heart Zones software, rather assessing the effect of monitoring HR with visual feedback in a group setting.

STU#: 00216223

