We will be using commercially available non-invasive, wireless HR monitors, such as the Scosche forearm monitor or other monitors with Bluetooth capability to pair with the Heart Zones platform. Scosche has a sensor with Velcro strap armband that is able to be cleaned with standard hospital cleaning procedures (Cavicide) between patient uses, yet is affordable, accessible and easy to use. Multiple heartrate monitors can be paired simultaneously and paired with a display such as an Apple IPad or other screen. Through visual display of multiple HRs in real time, it is feasible to use the Heart Zones application during a group rehabilitation session. The display monitors, HR monitors and Heart Zones platform will be stored in a locked cabinet accessible to research personnel for authorized use with this study.

PROCEDURES INVOLVED:

AIM1:

This will be conducted prior to enrollment of subjects into active phases of the study in order to understand baseline provider behavior regarding education to patients regarding intensity, monitoring of intensity and progression/modification of session intensity.

Observation of 15 sessions of each of the following conditions (total of 1500 minutes/condition):

1. Condition 1: Baseline Provider Behavior (prior to study beginning)
2. Condition 2: HR monitor on, no visual feedback
3. Condition 3: HR monitor on, visual feedback

Record number of instances in session the following occur:

- Provider provides education regarding HR/RPE/intensity
- Provider monitors HR/vitals
- Provider ask for RPE from patient
- Provider mentions target RPE/HR range
- Provider modifies task to reach target RPE/HR range

AIMS 2-5:

Screening Procedures & Consent

1. Potential subjects will be recruited from multiple settings across the continuum of rehabilitation as they are admitted.

STU#: 00216223

2. Once informed consent is obtained, screening will be performed to ensure inclusion criteria for study are met
3. Medical clearance for participation from supervising physician through online REDCap form.

2. Baseline

1. Participants will complete submax exercise test with licensed physical therapist in order to establish individualized HR intensities and zones.
 - i. Based on participant capability and timing, we will perform one or more of the submax tests or HR zone calculation methods for the individual based on clinical presentation and functional capacity.

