 2. Baseline measures and information will be collected from patient and medical record which include demographic information including gender, DOB, height, weight, co-morbidities, prior level of function, medical complications or concerns (pressure injuries, falls etc), precautions, admission level of function based on QI mobility items

STU#: 00216223

and outcomes measures in electronic medical record, reason for admission to rehabilitation.

3. Intervention:

1. Group and individual physical or occupational therapy sessions that are focused on endurance training (using upper and/or lower limb activities) which is a part of standard care for appropriate patients.
2. The only addition to usual standard care is the addition of a HR monitor that syncs with the Heart Zones software platform with or without visual feedback. Subjects will wear the HR monitor on their less sensory/motor impaired upper extremity.
3. There will be a continuous rolling enrollment, so some participants will receive HR feedback first while others will receive it on their second week.
4. Timing
 - i. Inpatient: 1 week of visual feedback of HR during group sessions and 1 week they will receive no feedback on their HR/zones.
 - ii. Day rehabilitation or community fitness: 2 weeks of visual feedback of HR and 2 weeks of no feedback due to fewer sessions per week.
5. Session Monitoring and Feedback
 - i. We will ask participants to rate their level of perceived exertion by using the Borg RPE Scale (6-20) at baseline, mid, and post each group session.
 - ii. Participants will answer 2 self-efficacy and confidence questions at the end of each session, rated from 0-100%.
 - iii. Subject's HR data from each session will be transferred for storage on a password protected computer accessible by approved lab staff only in order to perform summative data analysis, including peak HR, time in target HR zone, and average HR for whole session and for endurance training portion of the session.
6. We will monitor for occurrence of adverse events during sessions by assessing physiologic response to exercise, incidence of falls, etc.

4. Midpoint

1. We will collect information from their electronic medical record including new medical complications or concerns, their current functional level based on QI mobility items and outcome measures completed.

5. Post

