- Risk of loss of confidentiality will be minimized by not including personal identifying information on forms (participant will be assigned a research study number) and by conducting data collection in a private setting.

POTENTIAL BENEFITS TO PARTICIPANTS

There is likely no direct benefit to participants. Participation in this study will help researchers understanding if the use of visual feedback of HR in a group setting is feasible, efficacious and acceptable as care provided in a group model is a standard in rehabilitation.

DATA MANAGEMENT AND CONFIDENTIALITY

The analytic plan follows from the aims and the hypotheses. Descriptive statistics will be used to describe the participants and the data. Statistical tests will be utilized to assess for differences in individual outcomes baseline, mid and post through paired t-tests or appropriate non-parametric tests in consultation with a statistician. Data regarding the aims below may be analyzed for group sessions, individual sessions, and combined.

Aim 1: The null hypothesis is that there is no different in therapist behaviors to monitor/progress intensity prior to study, without visual feedback, or with visual feedback of participant's HR.

Aim 2: The null hypothesis is that there will be no difference in participant's ability to reach target intensity between sessions in which visual feedback of HR is provided and sessions where there is no visual feedback.

Aim 3: The null hypothesis is that there will be no increase in number of adverse events related to the use of Heart Zones with and without visual feedback.

Aim 4: The null hypothesis is that there will be no difference in participant exercise self-efficacy and confidence in reaching appropriate intensity when using visual feedback to no visual feedback during sessions.

Aim 5: The null hypothesis is that there will be no difference between submax exercise tests completed at baseline compared to post.

STU#: 00216223

Aim 6: The null hypothesis is that the providers will not feel the technology is appropriate, acceptable or feasible to use in a rehabilitation setting.

Data will be transferred to and stored on Shirley Ryan AbilityLab's REDCap system.

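### Aim 2 compares short blocks of mixed therapy sessions without logging or modelling session kind, which adds avoidable noise to the feedback contrast

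*Combined protocol and SAP*

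**What the plan says.** **Sessions.** Procedures Involved, Aims 2-5, Intervention, item 1, defines the monitored sessions: "Group and individual physical or occupational therapy sessions that are focused on endurance training (using upper and/or lower limb activities". They are standard care, and the only study addition is the monitor, with or without visual feedback. Inpatients have one week in each condition; day rehabilitation and community fitness participants have two. Because enrolment is rolling, some participants start with feedback and others without. No randomisation or ratio of orders is stated.

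**Session data.** Session Monitoring and Feedback lists perceived exertion, two self-efficacy and confidence questions, and heart rate summaries, "including peak HR, time in target HR zone, and average HR for whole session and for endurance training portion of the session". Discipline and limb mode are not listed.

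**Hypothesis.** Under Objectives, Aim 2 expects "higher mean HR and increased time in their individualized target HR zones when given visual feedback compared to no feedback during group sessions".

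**Analysis.** Data Management and Confidentiality plans "paired t-tests or appropriate non-parametric tests in consultation with a statistician". The only split by session type is optional: "Data regarding the aims below may be analyzed for group sessions, individual sessions, and combined". No term for session kind or period is given.

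**The concern.** The clinical schedule, not the study, decides how many sessions of each kind fall in a participant's feedback and no-feedback blocks. If arm-based and leg-based sessions, or PT and OT sessions, differ in typical heart rate, two blocks with different mixes will differ in mean heart rate whether or not feedback was on. With one or two weeks per block, such differences need not average out within a participant. They then enter the paired difference as error, and the planned test can neither see nor remove them.

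Precision is what is at stake in the first place: the same 90 participants carry less information on the feedback effect. Bias is possible only under two further conditions, examined in the working.

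**Working it through.** **The plan's own figure.** Participant Population(s) gives 90 to complete. No alpha, power, effect size or SD is stated, so 90 cannot be reproduced. For scale only, with an assumed two-sided alpha of 0.05 and 80% power, a paired comparison of 90 detects a standardised difference of (1.960 + 0.842)/√90 = 0.295.

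**Inputs.** From the documents: n = 90, the session kinds and the block lengths. Assumed, because the documents give none of them:
- D, the heart rate gap between two kinds: 5 to 15 bpm
- p, the share of one kind: 0.5
- m, the sessions per block: 5, with 2 as the low case
- S, the SD of a participant's block difference from all other sources: 8 or 10 bpm

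**Step 1: noise from chance mix.** If each session's kind is drawn independently, the added variance of the block difference is 2·D²·p(1−p)/m. At p = 0.5 and m = 5 this equals 0.1·D².

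| D (bpm) | Added variance | Added SD | Variance ratio, S = 8 | Variance ratio, S = 10 |
|---|---|---|---|---|
| 5 | 2.5 | 1.58 | 66.5/64 = 1.04 | 102.5/100 = 1.025 |
| 10 | 10 | 3.16 | 74/64 = 1.16 | 110/100 = 1.10 |
| 15 | 22.5 | 4.74 | 86.5/64 = 1.35 | 122.5/100 = 1.225 |

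For gaps of 5 to 10 bpm the variance rises by about 2.5% to 16%. With only 2 sessions per block the added variance is 0.25·D². The ratios for gaps of 5, 10 and 15 bpm are then 1.10, 1.39 and 1.88 at S = 8, and 1.06, 1.25 and 1.56 at S = 10.

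**Step 2: what that costs.** The detectable difference is 0.295 times the total SD. At m = 5, gaps of 5 and 10 bpm move it from 2.95 to 2.99 and 3.10 bpm when S = 10, and from 2.36 to 2.41 and 2.54 bpm when S = 8. Power for an assumed 3 bpm effect falls from 0.81 to 0.80 and 0.77 when S = 10, and from 0.945 to 0.937 and 0.911 when S = 8.

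**Step 3: when a trend in mix becomes bias.** Let d be the change in the share of one kind from the first block to the second, and q the share of participants who start without feedback. The bias in the feedback contrast is (2q − 1)·D·d. Take D = 10 bpm and d = 0.20, so the shift between blocks is 2 bpm, with S = 10:
- q = 0.5: bias 0, type I error 0.05
- q = 0.6: bias 0.2 × 2 = 0.4 bpm, type I error 0.066
- q = 0.7: bias 0.4 × 2 = 0.8 bpm, type I error 0.116

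Bias therefore needs both a trend in mix and uneven orders. The documents state neither. They expect improvement on the submaximal test (Aim 5) but do not say that session mix changes, and they do not assure balanced order.

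These figures concern mean heart rate. Time in zone would need its own inputs.

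**The case against.** Much can be said for the plan. Sessions must be endurance-focused, and average heart rate is also taken for the endurance portion alone. The Aim 2 hypothesis concerns group sessions, and group and individual sessions may be analysed apart. Each participant is their own control, and tests are chosen with a statistician. Averaging over the usual mix of care is a legitimate target. The noise model also leans high: p = 0.5 maximises p(1−p), a stable weekly timetable would add almost nothing, and sessions that use both arms and legs narrow the gap. All of this stands and keeps the point small. None of it removes differences in discipline or limb mode. Averaging sessions within a block is itself implied by a paired test, not written.

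Three stronger readings are tempting, and the documents do not support them.

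- **One zone serves every kind of session.** A reader might infer this from the separate walking, stepper and arm tests. The Background offers the arm test as a choice for people with limited leg function ("an alternative to determine aerobic capacity is to use the arm crank ergometer"), which is a choice per participant. The Baseline section allows several methods ("we will perform one or more of the submax tests or HR zone calculation methods for the individual"). Nothing says that a single zone is applied throughout.
- **A trend in mix biases the contrast by 1 to 4 bpm.** That is the shift between weeks for gaps of 5 to 20 bpm and a 20-point change in mix. It would equal the bias only if everyone had the same order, and the protocol says both orders occur. At 70:30 it becomes 0.4 × 1 = 0.4 to 0.4 × 4 = 1.6 bpm, and at 50:50 it is zero. No document supports a gap as large as 20 bpm.
- **The omission cannot be repaired later.** The privacy section provides for access to the medical record on care received, so discipline at least may be recoverable. No plan to recover it is stated.

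**Conclusion.** The point holds as a matter of precision. Session kind varies, discipline and limb mode are not listed data items, and the analysis has no term for kind or period. Under the assumptions shown (gaps of 5 to 10 bpm, 5 sessions per block, an even and independent mix, residual SD 8 to 10 bpm), the variance of the block difference rises by about 2.5% to 16%. Larger gaps or fewer sessions cost more; a stable weekly mix costs less. Members of a group share sessions, so their mixes may be correlated, which the calculation ignores.

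Bias from a trend in mix is conditional and secondary. It scales with the imbalance in block order, and its root is the unspecified order together with the missing period term. This is a minor but worthwhile improvement, not a threat to the validity of Aim 2.

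**What to change.** **Record.** For each session, log from the therapy schedule the discipline and whether it is group or individual. Log limb mode only where it is set before the session; the documents do not say that it always is.

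**Analyse.** Fit Aim 2 at session level with feedback condition, period (first or second block) and scheduled kind as fixed effects, and participant and participant-by-condition as random effects. The second random effect stops repeated sessions within a block from being counted as independent evidence on feedback. The period term absorbs an average trend, provided both orders occur. Add a sensitivity analysis without kind.

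**Do not adjust for the activity actually performed.** Aim 1 expects providers to change sessions when feedback is shown, so that adjustment could remove part of the effect under study.

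**Cost.** One extra field per session, a short addition to the analysis plan and a few degrees of freedom.

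### Aim 3 compares adverse events with and without the HR display, but the display may help staff notice HR-related events, so an observed increase could not be separated from better detection

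*Combined protocol and SAP*

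**What the plan says.** **How events are found.** Under Procedures Involved, Aims 2-5, Intervention item 6: "We will monitor for occurrence of adverse events during sessions by assessing physiologic response to exercise, incidence of falls, etc". No event definition, threshold, checklist or assessor is given, and no rule says that detection must be the same in both conditions.

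**What is compared.** Under Data Management and Confidentiality, the Aim 3 null is "no increase in number of adverse events related to the use of Heart Zones with and without visual feedback". The Aim 3 hypothesis in Objectives names no comparator: "We hypothesize the technology will be safe without an increase in number of adverse events throughout their rehabilitation stay". The safety item under Study Endpoints refers only to recording incidence.

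**What differs between conditions.** The monitor is worn throughout and the display is switched. Inpatients have "1 week of visual feedback of HR during group sessions and 1 week they will receive no feedback on their HR/zones"; day rehabilitation and community fitness participants have two weeks of each. For providers, Aim 1 describes the no-feedback condition as "when providers know HR monitoring is occurring but without visual feedback".

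**What is expected of providers.** Aim 1 hypothesises that "providers will modify their behavior in the number of times they ask about intensity, adjust session intensity or provide education regarding intensity when visual feedback" appears, compared with none. The Aim 1 procedures also count provider checks of HR or vitals as a behaviour recorded in each condition.

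**What is stored.** Intervention item 5 iii: "Subject's HR data from each session will be transferred for storage on a password protected computer". The analysis uses it lists include peak HR, time in target zone and average HR. No safety use is mentioned.

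**The concern.** The displayed HR is the intervention, and it is also a source of information for the safety outcome. If an event is recognised because somebody sees an abnormal HR, it is more likely to be recognised when HR is on a screen. The two counts in the Aim 3 comparison would then differ in how thoroughly events were looked for as well as in how often they occurred.

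What is at stake is the reading of an observed increase. It could mean that feedback pushes participants to an intensity that causes more events, or only that staff saw more of what was already happening. A non-inferiority margin or a different test would not separate the two, because the bias is in the data before any test is applied.

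**Working it through.** **No figure to reproduce.** The documents state no adverse event rate, margin, alpha or power for Aim 3, and the sample size of 90 comes without inputs. The check is therefore a reading of the text followed by an illustration.

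**Reading the text.**
1. Events come partly from physiologic response observed in the session (Intervention item 6).
2. HR is part of that response, and the display is what changes between periods (Intervention items 2 and 4).
3. In the no-feedback condition providers are described as being without visual feedback (Objectives, Aim 1). Applying this to the Aim 3 sessions is an inference, though a natural one because the conditions carry the same labels.
4. The protocol predicts more provider attention to intensity when the display is on (Objectives, Aim 1).
5. No stated rule equalises detection.

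**Illustration; every input is assumed.** Let *f* be the share of events whose recognition depends on seeing HR, and *d0* the probability that such an event is noticed without the display. Take true risk and exposure as equal in the two conditions, and detection under feedback as complete. Then

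observed rate ratio = 1 / (*f* × *d0* + 1 − *f*).

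For *f* = 0.5: *d0* = 0.9 gives 1/0.95 = 1.05; *d0* = 0.75 gives 1/0.875 = 1.14; *d0* = 0.5 gives 1/0.75 = 1.33.

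| *f* | *d0* = 0.9 | *d0* = 0.75 | *d0* = 0.5 |
|---|---|---|---|
| 0 | 1.00 | 1.00 | 1.00 |
| 0.25 | 1.03 | 1.07 | 1.14 |
| 0.50 | 1.05 | 1.14 | 1.33 |
| 0.75 | 1.08 | 1.23 | 1.60 |

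**Chance of a false increase.** Assume Poisson counts, 18 true events per condition, *f* = 0.5, and a one-sided exact conditional binomial test at 0.05 (the plan names only paired t-tests or non-parametric alternatives). The probability of declaring an increase when there is none is 0.036 with equal detection, 0.079 at *d0* = 0.75 and 0.158 at *d0* = 0.5.

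**With equal detection.** Setting *d0* = 1 returns the ratio to 1.00. The false-increase probability is then 0.032, 0.036 and 0.040 at 9, 18 and 45 true events per condition.

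**The case against.** The strongest reply is that the documents never count an HR excursion as an adverse event. The harms listed under Risks to Participants are armband discomfort, skin breakdown, fatigue or soreness, chest pain or breathlessness, falls and loss of confidentiality. None needs an HR screen to be noticed. Providers are to watch participants closely in every session, perceived exertion is collected at three points in each group session whatever the condition, and the medical record is reviewed at midpoint and at the end. This stands. It means *f* may be low, and it confines the point to an unknown subset of events. It does not remove the point: physiologic response is named as a means of detection and left undefined, the watching providers are those whose attention is expected to change with the display, and record review is not described as capturing brief in-session HR excursions.

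A reader might go further than the documents allow in three ways.

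- **That without the display an abnormal HR is noticed only by a spot check.** The timing section withholds feedback from participants. It does not say that staff cannot see live HR. The provider side rests on the Aim 1 wording alone.
- **That the log is reserved for efficacy.** The listed uses are introduced as examples, and peak HR is already to be derived from every session.
- **That the ratio is as large as 0.9/0.5 = 1.8 or 0.9/0.7 = 1.29.** Those figures hold only if every counted event depends on seeing HR.

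It is also fair to say that the contrast between conditions appears only in the Aim 3 null, and loosely there.

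**Conclusion.** The point holds for events recognised through HR. Followed as written, the plan allows detection of those events to be higher under feedback, so an observed increase in Aim 3 could not be attributed to risk. The size is unknown. Under the assumptions above the spurious ratio is about 1.05 to 1.33 if half of events depend on seeing HR, and 1.00 if none do. Falls, symptoms, skin events and record-based complications are largely untouched.

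A reader might infer that neither possible result would answer Aim 3. The documents do not support that. The null concerns an increase, and this bias inflates the feedback count. If the counts are nevertheless similar, the result is conservative with respect to this bias for the events counted. The ambiguity lies in an observed increase.

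The conclusion rests on the Aim 1 description of the no-feedback condition also applying to the Aim 3 sessions, and on at least some counted events being recognised through HR.

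**What to change.** For the Aim 3 comparison, add a summary of HR excursions:

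- Compute it by one prespecified, scripted rule from the HR log already stored for every session, applied identically to both conditions and without reference to condition.
- Use whatever individual limit the medical team has already recorded. The documents need reconciling here: Objectives implies that every participant has a safe HR range from the medical team, while the Baseline section treats strict medical HR guidelines as rare. The sponsor should state which existing limit applies to each participant.
- Report excursions per monitored session, by condition, as their own category and not as clinical adverse events.
- Report falls, symptoms, skin events and record-based complications separately, by condition.
- Prespecify one artefact rule for the sensor trace and apply it equally to both conditions.

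Live monitoring for care stays as planned.

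**Cost.** Plan wording, a short script and one additional summary, with no new data collection. The downside is that more HR excursions will be reported in total than live observation would yield, and some may be sensor artefact.
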